A total of twenty patients will be recruited and enrolled in this study. All twenty patients will wear the Spacelabs Ambulatory Blood Pressure Monitor Model No. 90207 for 24 hours a total of two times – at baseline and following one month of the patient receiving their change in drug therapy. The randomization process to assign patients to either the group receiving chronotherapy or the group receiving therapy changes based on ABPM will be determined by placing strips of paper with the unique patient codes into an envelope and picking out numbers. One group will receive a shift in the timing of one of their antihypertensive medications to nighttime dosing without consulting their ABPM results. The other group will receive a modification in their antihypertensive medication regimen based on their ABPM results; modification in therapy would entail a shift in dosing of an existing blood pressure medication to nighttime for non-dippers while dippers would receive a change in regimen (change in strength of medication, addition of new medication, etc.) selected according to normal standard of care management of hypertension. Any specific changes to medication regimen outside of altering the timing of dose administration is not dictated by this study and will be based on usual process of treating uncontrolled hypertension patients and clinical expertise of the primary care physician. All subjects will be instructed on the operation of the ABPM and properly fitted with the monitor. Prior to leaving the office, they will undergo a minimum of one blood pressure reading to ensure adequate functioning of the monitor. They will also be given an information sheet detailing what to expect while using the ABPM as well as a diary to record the time of their meals, their medication administration, bedtime, time of awakening, any symptoms if they occur, and any period of stress or mood-altering activity that may affect the blood pressure reading. Patients will return the following day after wearing the monitor for 24 hours so that the

data can be collected, and based on the group to which the patient was assigned, drug therapy may be modified according to the analysis of the ABPM results and their diary of activity. Requirements for a satisfactory ABPM involves having a minimum of 20 valid daytime measurements, a minimum of 7 measurements while asleep, and at least 70% of the measurements obtained at least every 30 minutes or more frequently throughout the 24-hour period.⁴

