
Follow-up will occur for both treatment groups after one month of initiating their modified anti-hypertensive regimen to see how changes in drug therapy impact their blood pressure control. Patients will arrange for their follow-up 24-hour ABPM screening. The procedure from the first ABPM screening will be repeated, and the patient will return the following day to remove the monitor, return their ABPM diary, and submit their ABPM results for analysis.

[figure not shown]

Chart 1: Flow chart demonstrating process for conducting the study

Aside from patients receiving ABPM, all patients will receive standard care in managing their hypertension involving hypertension follow-up appointments and adjustments in therapy to achieve adequate blood pressure control. For those patients who are in the group whose changes in therapy will be determined after evaluating their ABPM results, patients found to be dippers and would not benefit from the switch in dosing to nighttime will receive changes in therapy as would be expected in clinic as standard care if a dose increase/medication change is warranted. Clinical data will be obtained from standard blood pressure monitoring equipment provided by the clinic. Therefore, this study will not result in additional charges associated with the treatment and care of the patient.

Data collection will include age, sex, race, height, weight, comorbidities (Diabetes Mellitus, hyperlipidemia, history of stroke, transient ischemic attack, myocardial infarction, etc.), antihypertensive therapies including dosing schedule at baseline as well as after modification from receiving either treatment option, complete medication history including over-the-counter and herbal medications, whether or not the patient uses a home blood pressure monitor (yes or no), lifestyle history including caffeine and alcohol intake and tobacco use, number of years since HTN diagnosis, whether or not patient was at blood pressure goal at the follow-up visit at one month after initiating change in therapy (yes or no), and the blood pressure readings from the ambulatory blood pressure monitor at baseline and one month post initiation of change in drug therapy. Data will be obtained through EPIC, including the patient-recorded data such as the diary of activity during the 24 hours wearing the ABPM which will be scanned into EPIC. The results of the ABPM will be obtained from the ABPM software and may be scanned into EPIC for ease of access.

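### Does timing the one-month assessment from the therapy change leave some ABPM-arm dippers with no outcome date and no place in the analysis?

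*Combined protocol and SAP*

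**What the plan says.** All references are to the combined protocol and SAP.

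**Timing.** The follow-up paragraph of section 6 reads "Follow-up will occur for both treatment groups after one month of initiating their modified anti-hypertensive regimen". Earlier in section 6, all twenty patients wear the monitor twice, "at baseline and following one month of the patient receiving their change in drug therapy". The Abstract (section 3), the Specific Aim (section 5), the data-collection paragraph of section 6 (for goal status and again for the ambulatory readings) and the analysis plan use the same origin.

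**Who has a change.** For the night-time arm: "One group will receive a shift in the timing of one of their antihypertensive medications to nighttime dosing without consulting their ABPM results". For the ABPM arm, the same paragraph specifies a "shift in dosing of an existing blood pressure medication to nighttime for non-dippers while dippers would receive a change in regimen". Section 5 likewise says, without condition, that the ten ABPM-arm patients have their therapy modified. The standard-care paragraph of section 6 is less firm. There, dippers "will receive changes in therapy as would be expected in clinic as standard care if a dose increase/medication change is warranted". At the visit the day after the monitor is fitted, "drug therapy may be modified according to the analysis of the ABPM results and their diary of activity", depending on the assigned group. Any change other than timing "will be based on usual process of treating uncontrolled hypertension patients and clinical expertise of the primary care physician".

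**Analysis.** Section 6 plans a paired t test on each patient's change in blood pressure, and a chi-square or Fisher test on the number at goal in each group. It names no analysis set for either arm.

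**The concern.** A clock that starts at the therapy change needs a therapy change. If the conditional wording for dippers governs, an ABPM-arm dipper whose regimen is left alone has no start date, so neither the second ABPM nor the goal assessment can be dated from the text. No patient in the night-time arm can be in that position, and whether an ABPM-arm patient is in it is settled after randomisation.

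Such a patient is not far-fetched. Entry needs a reading above 130/80 mmHg but no ambulatory confirmation (section 5), and the Background (section 4) gives white-coat hypertension as the main diagnostic use of ABPM.

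If analysts dropped these patients because they had no date, the comparison would no longer be ten against ten as randomised. The ABPM arm would also lose the patients in whom monitoring led to a decision to change nothing, which is part of what the pilot is meant to assess.

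**Working it through.** **1. Count of the time origin.** Statements of the one-month assessment: Abstract 1, Specific Aim 1, section 6 monitoring paragraph 1, follow-up paragraph 1, data collection 2, analysis plan 1. Total 1 + 1 + 1 + 1 + 2 + 1 = 7. All seven count from the change in therapy; none counts from randomisation or the baseline monitor.

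**2. Who could lack a change.** Night-time arm: nobody. ABPM-arm non-dippers: nobody. ABPM-arm dippers: nobody under section 5 and the group-assignment paragraph of section 6; possibly some under the standard-care paragraph. The permissive verb at the return visit adds little, because that sentence covers both groups and only one of them is modified from ABPM results. The conflict therefore rests on one conditional clause.

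**3. How likely at least one is.** The documents give no rate. If a share q of the ABPM arm were unchanged dippers, the chance of at least one in ten is 1 − (1 − q)^10. This gives 0.40 for q = 0.05, 0.65 for q = 0.10 and 0.89 for q = 0.20 (q assumed). The case cannot be dismissed as impossible.

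**4. What a common anchor would change.** The obvious alternative origin is return of the baseline monitor. Section 6 already places modification at that visit. For a patient changed there, one month from change and one month from monitor return are the same date, so nothing moves. For an unchanged patient the anchor supplies a date. No new drug exposure has begun in that patient, so a few days either way has no bearing on time on treatment.

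**5. Who is counted.** The second ABPM is required in all twenty (sections 5 and 6), the paired change is taken for every patient, and goal attainment is counted by assigned group. No sentence removes a patient for lack of a change. The natural reading is 10 against 10.

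**6. Size if patients were nevertheless dropped.** Assume k = 1 to 3 unchanged patients and a = 3 to 7 of 10 truly at goal in each arm.

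- Dropped patients all at goal: (a − k)/(10 − k). With a = 5, k = 2: 3/8 = 37.5% against 50%.
- Dropped patients none at goal: a/(10 − k). With a = 5, k = 2: 5/8 = 62.5% against 50%.
- Smallest shifts: a = 7, k = 1 gives 6/9 = 66.7% against 70% (−3.3 points); a = 3, k = 1 gives 3/9 = 33.3% against 30% (+3.3).
- Largest shifts: a = 3, k = 3 gives 0/7 against 30% (−30 points); a = 7, k = 3 gives 7/7 against 70% (+30).
- Fisher two-sided, 3/8 against 5/10: p = 0.66.
- Mean fall: if unchanged patients have zero change and the rest fall by d, the overstatement is d − d(10 − k)/10 = dk/10. For d = 5 to 10 mmHg this is 5 × 1/10 = 0.5 to 10 × 3/10 = 3.0 mmHg.
- Standard error of the difference in means, SD × √(1/10 + 1/(10 − k)): 4.59 mmHg (SD 10, k = 1) to 7.39 mmHg (SD 15, k = 3), with both SDs assumed.

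**7. Size if all are kept.** The denominators stay at 10 and 10, and the exclusion effect is 0 for any k.

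**The case for a change.** The best case for amending is that writing the rule down is cheap: a few sentences and two dates per patient. Section 9 also has the investigators analysing data as they accrue, so a rule left unwritten could be settled with results in view. A pilot is read on its estimates, so a shift of up to 30 points in a proportion matters even where no test would detect it. Monitor return is an event every patient shares.

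Some of this stands. The two statements on dippers do differ, and an unchanged dipper has no written date. The rest does not carry an amendment. The lack of a named analysis set applies to both arms, and the nearest text keeps everyone. Dropping a patient would go against the requirement for a second ABPM in all twenty, so it is not an open choice left by the plan. It might also be argued that a dipper's clock starts late because the change follows the physician's usual process. That wording governs which change is made, not when.

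The number of unchanged patients can be recovered without new data, since section 6 collects therapies and dosing schedules at baseline and after modification. Timing from the change also has a sound purpose: it gives patients equal time on the new regimen.

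**Conclusion.** No change to the plan follows. This is missing detail that a competent analyst fills in one obvious way: assess an unchanged patient one month after the baseline monitor is returned, and count all twenty in their assigned groups. Done that way, the exclusion effect is zero, and no date moves for patients changed at the return visit. The 3 to 30 point and 0.5 to 3.0 mmHg shifts arise only with assumed numbers of unchanged patients, assumed outcomes and an exclusion the plan does not contain. Their direction is unknown. The mean shifts are smaller than one standard error of the difference, and the worked comparison of proportions is far from significant.

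The conclusion rests on two readings: that modification takes place at the monitor-return visit, and that the text on all twenty patients means what it says. Chart 1 was not available and may already show the path for these patients. Whether every dipper receives a change is a clinical matter on which the two paragraphs of section 6 must be reconciled by the investigators. The analysis is the same under either answer.

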Management of Uncontrolled Hypertension (HTN)

NCT02922023

10/26/2022

Protocol

1. Title:

Management of Uncontrolled Hypertension: Ambulatory Blood Pressure Monitoring and Subsequent Modification of Therapy or Shifting Anti-hypertensive Medication to Night-time Dosing

2. Investigators:

Principal Investigator:

[name] [name].
Clinical Assistant Professor
Department of Pharmacotherapy and Translational Research

Sub-Investigators:

[name]
[name].
UF College of Pharmacy

[name].
Internal Medicine Physician
UF Health Internal Medicine – Medical Plaza

3. Abstract:

Ambulatory Blood Pressure Monitoring (ABPM) and its role in clinical practice continues to evolve. ABPM allows providers to obtain blood pressure readings over a 24hour period, to assess blood pressure at night to determine “dipping” status, and to evaluate the efficacy of anti-hypertensive therapy. By utilizing ABPM in uncontrolled hypertension patients in clinical practice, modifications in drug therapy can be based on a more comprehensive and accurate depiction of the patient’s overall blood pressure control throughout the day. Although, theoretically, an assessment of the 24-hour blood pressure of a patient prior to adjusting drug therapy should yield better blood pressure control, we would like to carry out a pilot study to investigate whether the modifications in therapy based on ABPM and the resulting impact on blood pressure control would be substantially different from simply switching the dosing of medication to night-time.

In this study, we will compare chronotherapy to ABPM. Data collected will include hypertension drug therapy regimen prior to and during the study, timing of medication administration, and dose, along with the patient’s office blood pressure values prior to study and one month after modification in therapy. This will enable us to explore

whether it is a practical endeavor to implement ABPM as a routine process for all uncontrolled hypertension patients or whether ABPM does not seem to provide considerable value over shifting the timing of drug administration.

4. Background:

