ABPM is primarily used to diagnose white coat hypertension, however, ABPM may be used to assess efficacy of blood pressure treatment by evaluating the patient's blood pressure control over a 24-hour period.⁵ The capability to provide night-time readings during sleep sets it apart from office blood pressure readings and home blood pressure readings, and it provides information for the determination of dipping status. Non-dipping status has been associated with target organ damage including left ventricular hypertrophy, microalbuminuria, cerebrovascular disease, congestive heart failure, vascular dementia, stroke, and myocardial infarction.⁶ The frequency of non-dipper patterns tends to be higher in hypertension that is secondary to specific medical conditions such as chronic renal failure, diabetes, and autonomic nervous system dysfunction than in uncomplicated primary hypertension. A study also showed that the percentage of patients that ingest all their antihypertensive medications in the morning was significantly greater in non-dippers than the dippers suggesting that non-dipping among treated patients is partly due to lack of 24-hour therapeutic coverage when administered in the morning.⁹

stages hypertension as Stage 1 with pressure. Adults between the ages of 18 and 59 years old or any adult with diabetes or chronic kidney disease are considered hypertensive with three consecutive blood pressure readings above 140/90 mmHg.⁷ Resistant hypertension is defined as blood pressure that remains above the goal of 130/80 mmHg despite the use of three anti-hypertensive agents at optimal doses including a diuretic, if possible, or blood pressure that is controlled with the use of four or more antihypertensive drugs.⁸ Although non-adherence is a common contributing factor to pseudo-resistant hypertension, it remains difficult to apply a simple, inexpensive, and reliable method in the clinical setting to quantify this factor when investigating potential causes for resistant hypertension.⁸ Additionally, seemingly resistant hypertension may be related to inadequate night-time blood pressure control leading to elevated blood pressures during sleep as well as a higher-than-normal morning rise/spike upon awakening.⁶

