move a medication to bedtime dosing, without relying on ABPM. Given that the initial cost associated with purchasing ABPM equipment (\$2500-\$5000) and software (\$2000-\$3000)¹¹ is not inconsequential, we propose this pilot study to determine whether ABPM in clinical practice is an investment that results in significant difference in blood pressure control when compared with chronotherapy.

5. Specific Aim:

We propose to conduct a pilot study to determine whether the incorporation of Ambulatory Blood Pressure Monitoring (ABPM) as routine procedure in clinic for uncontrolled hypertension influences how anti-hypertensive drug therapy is modified or if simply shifting the dosing of anti-hypertensive medications to night time achieves similar results. We will enroll 20 participants with uncontrolled hypertension, who are prescribed 3 anti-hypertensive medications. All twenty patients will undergo 24-hour blood pressure monitoring with ABPM at baseline and one month after change in therapy has been initiated; ten of the patients will be randomized to receive a shift in dosing schedule of anti-hypertensive medication to night-time without utilizing their ABPM results while the remaining ten will receive modifications in therapy based on their ABPM results and dipping status. The results of this study will assist in assessing the feasibility and benefits of the incorporation of ABPM into the routine management of hypertension.

6. Research Plan:

Patient eligibility

Inclusion criteria

1. Age \geq 18 years
2. Blood pressure of $>130/80$ mmHg
3. Currently receiving 3 anti-hypertensive agents, one of which is a diuretic, for at least six weeks

Exclusion criteria

1. Vulnerable populations
 - a. Pregnant women
 - b. Prisoners
 - c. Cognitively impaired persons
 - d. Economically and/or educationally disadvantaged
 - e. Human fetuses and neonates
 - f. Patients who work night-shift
 - g. Children
 - h. Conditions with visual field deterioration (Anterior Ischemic Optic Neuropathy, Glaucoma, Optic Nerve Disorders)

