Descriptive statistics, including REDCap (Research Electronic Data Capture) will be used to analyze patient data. Unique patient codes will randomly be assigned to each patient participating in the study through REDCap, and the patient code will serve as the identity of the patient throughout the study. The master list linking the patient codes to the specific patient names will be kept as a physical copy that will remain in a locked filing cabinet in HPNP Room 3313, and only the investigators will have access. The list will be shredded at the conclusion of the study. All electronic files containing clinical information will have PHI removed, and data will be stored on encrypted, password protected files accessed on a UF server. No information will be released to any person or agency without consent of the subject except as required by law.

Analysis plan for initial questions: To determine whether there is a difference in achieving blood pressure goal by using ABPM or chronotherapy.

Descriptive statistics will be carried out using paired t test (changes in blood pressure from baseline vs after 1 month of change in drug therapy for each patient) and Chi-square test or Fisher's Exact Test (amount of subjects from each group that achieved blood pressure goal).

For researchers other than those named on the protocol, use of the data and samples procured under this study will require approval from the PIs of this study in addition to the IRB.

7. Possible Discomforts and Risks:

Risk to the patient from participation in this study is minimal. Participants will not be subjected to processes beyond what is required for obtaining a satisfactory 24-hour blood pressure evaluation and required for routine monitoring of hypertension. Risks of using the ABPM are none. Slight discomfort may occur while wearing the ABPM device throughout the 24 hours as the device periodically inflates, and there may be modest sleep disturbances at the intervals when blood pressure readings are taken. Aside from

the aforementioned, participants will not have any additional discomforts beyond those associated with routine management of their hypertension.

8. Possible Benefits:

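### The only between-arm test uses a blood pressure goal with no assigned source or cut-off, and no between-arm comparison of the 24-hour ABPM collected in both arms is stated

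*Combined protocol and SAP*

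**What the plan says.** The analysis text in Section 6 asks whether the arms differ in reaching blood pressure goal. It names two tests:

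- a paired t test of each patient's change from baseline to one month;
- a Chi-square or Fisher's exact test on the "amount of subjects from each group that achieved blood pressure goal".

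The data list in Section 6 defines the goal item only as "whether or not patient was at blood pressure goal at the follow-up visit at one month after initiating change in therapy", answered yes or no. As a separate item it lists "the blood pressure readings from the ambulatory blood pressure monitor at baseline and one month post initiation of change in drug therapy". At follow-up, patients wear the monitor again and "submit their ABPM results for analysis".

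The Abstract (Section 3) says the data will include "office blood pressure values prior to study and one month after modification in therapy". Section 6 also states: "Clinical data will be obtained from standard blood pressure monitoring equipment provided by the clinic".

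Two places give a possible cut-off. The Background (Section 4) defines resistant hypertension as "blood pressure that remains above the goal of 130/80 mmHg" on three suitable drugs, and the second inclusion criterion is "Blood pressure of $>130/80$ mmHg".

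**The concern.** Two gaps meet in one analysis. First, the outcome that answers the study question is not fully defined. The Background gives white-coat and masked hypertension as reasons to use ABPM, and in both conditions office and ambulatory pressure disagree. The same patient could be at goal by one source and not by the other, so the answer can depend on a choice the plan does not make.

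Second, the richest data in the trial have no stated between-arm use. One arm moves a drug to night-time without reference to ABPM; the other is managed from it. The Background says night-time readings are what set ABPM apart from office and home readings. Those readings exist for both arms at both times, but the plan does not say that the arms will be compared on them. At stake is whether the pilot can describe an arm difference in 24-hour and night-time pressure at all.

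**Working it through.** **Which analyses compare the arms?** The paired t test contrasts each patient with himself or herself, so even run separately by arm it gives no between-arm estimate. The Chi-square or Fisher test does compare arms, but only on the yes/no goal. No third analysis is named.

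**What is the goal measured on?**

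| Text | Points to | Tied to the goal item? |
|---|---|---|
| Section 3, office values before and at one month | office | no |
| Section 6, clinic equipment | office, but the next sentence concerns charges | no |
| Section 6, data list | ABPM is the only numeric blood pressure item | no; listed separately from the goal |
| Section 6, follow-up procedure | ABPM, submitted for analysis | no |

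**What is the cut-off?** 130/80 is the only figure the documents call a goal (Section 4), and it matches the entry threshold (Section 6). Section 8 speaks of patients' goals in the plural, which leaves individual goals possible. Nothing in the text assigns either to the goal item. Chart 1 is not visible and could not be checked.

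**What would a continuous ABPM comparison add?** The plan states no alpha, SD, effect or goal rate, so there is no figure to reproduce. Inputs:

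- from Section 5: n = 10 per arm;
- assumed: two-sided 0.05, Normal follow-up systolic pressure, arm means 135 and 125 mmHg (difference d = 10), SD 8 to 15, cut-off 130, no missing recordings, no baseline adjustment.

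Formulas:

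- Continuous: noncentrality = d / (SD × √(2/n)), 18 df, critical t = 2.101. At SD 10: 10 / (10 × 0.447) = 2.24, giving power 0.56.
- Goal rates: Φ((130 − mean)/SD). At SD 10: Φ(−0.5) = 0.31 and Φ(0.5) = 0.69. Power is the sum of binomial probabilities over all 10 v 10 tables with p ≤ 0.05.
- 95% confidence interval half-width for the difference: 2.101 × SD × √(2/10) = 0.94 × SD.

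| SD (mmHg) | Goal rates | Fisher | Chi-square, uncorrected | t test | CI half-width (mmHg) |
|---|---|---|---|---|---|
| 8 | 27% v 73% | 0.36 | 0.55 | 0.75 | 7.5 |
| 10 | 31% v 69% | 0.22 | 0.39 | 0.56 | 9.4 |
| 12 | 34% v 66% | 0.15 | 0.28 | 0.42 | 11.3 |
| 15 | 37% v 63% | 0.09 | 0.20 | 0.29 | 14.1 |

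On the same readings, the comparison of means has about 2 to 3 times the power of Fisher's test and about 1.4 to 1.5 times that of the uncorrected Chi-square. This measures the cost of dichotomising. It says nothing about how office and ambulatory readings differ.

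**The case against.** The strongest reply is that this is a 20-patient pilot, its tests are labelled descriptive, and goal attainment in clinic is a legitimate outcome for a question about routine practice. On that view one sentence naming source and cut-off would be enough. Much of this stands. Low power is not an error here, and ABPM as the main source is an improvement rather than the correction of a mistake. But that one sentence would still leave the ambulatory readings without a stated between-arm use.

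Four stronger readings are tempting, and the documents do not support them.

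- *The endpoint is office pressure, so the trial cannot see the night.* The abstract leans that way. However, the detailed data list contains no office value, and the clinic-equipment sentence leads into a remark about charges. The source is open.
- *There is no cut-off at all.* 130/80 is a reasonable inference. What is missing is its assignment to the endpoint.
- *The definition will be chosen after results are seen.* Section 9 has the investigators analysing data as they arrive. But goal status is recorded visit by visit, and a de-identified dataset goes to a statistician. That limits the risk without removing it.
- *One reclassified patient overturns the result, so the outcome is biased.* At an assumed 0.05 level, 34 of the 121 possible 10 v 10 tables are significant by Fisher's test; 14 lose significance when one patient is moved and 22 when two are. These are worst-case counts: the patient sits in the more damaging arm and moves toward the other arm's rate. If significance must be lost whichever arm is affected, the counts are 10 and 18. They reflect ten per arm, would apply equally to an ABPM goal, and are no evidence of bias.

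**Conclusion.** The concern holds in this form: the sole between-arm test rests on a goal whose source and cut-off are not assigned, and no between-arm comparison of the ABPM readings is stated, although they are collected twice in every patient and the question concerns night-time dosing. It is a worthwhile, inexpensive improvement rather than a fatal flaw.

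The direction and size of any effect of the unassigned source cannot be derived from the documents. The power and interval figures are illustrations resting on the assumed means, SDs and alpha. Even the better analysis would be imprecise: at SD 10 the unadjusted interval is about ±9 mmHg. The estimate and its interval therefore matter more than the p value. Confidence is medium, because Chart 1 cannot be seen and part of the gap could be closed by inference.

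**What to change.** Before any data are analysed:

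1. Add a between-arm comparison of follow-up 24-hour mean ABPM, adjusted for the baseline ABPM value, reported as an estimate with a 95% confidence interval. Report the night-time mean the same way, because a 24-hour mean does not isolate the night.
2. Base the goal comparison on ABPM, with one cut-off chosen by the investigators in advance and applied to all patients. Report how many in each arm were already at that goal at baseline.
3. Report goal attainment on office pressure as secondary.
4. State how recordings that fail Section 6's validity requirements (20 valid daytime readings, 7 asleep, 70% of readings at the required frequency) are handled.

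No new ambulatory measurement is needed; the monitor is already worn twice. The cost is a few sentences of analysis text and one stated cut-off. There are two downsides: invalid recordings will leave some outcomes missing, which counts with ten per arm, and some patients may already be at ABPM goal at baseline and so add little to the goal comparison. The baseline-adjusted continuous comparison is less exposed to the second.

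### Continuous blood pressure gets only a within-patient paired t test, so the plan never estimates the ABPM-versus-chronotherapy difference in pressure

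*Combined protocol and SAP*

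**What the plan says.** The analysis plan near the end of Section 6 (Research Plan) is one question and one sentence of methods. The question is "To determine whether there is a difference in achieving blood pressure goal by using ABPM or chronotherapy". The methods are a "paired t test (changes in blood pressure from baseline vs after 1 month of change in drug therapy for each patient" for pressure, and a Chi-square or Fisher's exact test for the "amount of subjects from each group that achieved blood pressure goal".

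The aims elsewhere are wider. The end of Section 4 (Background) asks whether ABPM "results in significant difference in blood pressure control when compared with chronotherapy". Section 5 (Specific Aim) asks whether "simply shifting the dosing of anti-hypertensive medications to night time achieves similar results". The Abstract also describes the study as a comparison of the two approaches.

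The data for such a comparison are planned: "All twenty patients will undergo 24-hour blood pressure monitoring with ABPM at baseline and one month after change in therapy has been initiated". Section 6 sets quality criteria for a recording ("minimum of 20 valid daytime measurements, a minimum of 7 measurements while asleep", plus a 70% rule), and at follow-up patients "submit their ABPM results for analysis".

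**The concern.** The paired t test asks whether pressure changed from baseline. The plan does not say whether it is pooled over 20 patients or run separately in each arm of ten, or which pressure enters it (office, 24-hour, daytime, night-time, systolic or diastolic).

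- **Pooled**, it has no arm term. It describes the average change under the two strategies together and cannot separate them.
- **Run by arm**, it gives two p-values and neither a test nor an estimate of the difference between arms. Setting one significant and one non-significant result side by side is not a comparison.

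The goal count is then the only randomised comparison. It reduces each patient to yes or no and uses little of the ABPM data. Similarity cannot be judged from a before-after test, nor from a non-significant count at 10 against 10. It needs an arm difference with a confidence interval. Both the Abstract and Section 4 tie the result to whether ABPM is worth adopting, so the lack of an effect size matters.

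**Working it through.** **Inputs.** From the documents: 20 patients, 10 per arm, two ABPM recordings each (Sections 5 and 6). The plan states no alpha, SD, effect size or goal rate and has no power calculation to reproduce. Everything else is assumed: two-sided 5% level, SD of change 10–15 mmHg, baseline to one-month correlation r = 0.5. At r = 0.5 the SD of change, SD·√(2(1−r)), equals the SD at a single time, so one SD serves both analyses.

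**1. Paired test by arm, identical strategies.** Power in one arm comes from the noncentral t with 9 df and noncentrality fall/(SD/√10). With independent arms, the chance that exactly one is significant is 2p(1−p).
- Fall 4, SD 15: noncentrality 0.84, p = 0.118; 2 × 0.118 × 0.882 = 0.208.
- Fall 10, SD 10: noncentrality 3.16, p = 0.803; 2 × 0.803 × 0.197 = 0.316.
- Fall 8, SD 12: noncentrality 2.11, p = 0.469; 2 × 0.469 × 0.531 = 0.498.

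Over falls of 4–10 mmHg and SDs of 10–15 the range is 21–50%.

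**2. Pooled paired test, identical strategies.** With 19 df, a fall of 8 and SD 12, noncentrality is 8/(12/√20) = 2.98 and power is 0.807. Over the same ranges of fall and SD it runs from 21% to 99%. In every case the true arm difference is zero.

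**3. Goal count, true arm difference of 1 SD.** Shifting a normal outcome by 1 SD moves the goal rate from 30% to 68.3%, 40% to 77.2% or 50% to 84.1%. Exact enumeration of 10 against 10 gives:

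| Lower-arm goal rate | Fisher | Uncorrected chi-square |
|---|---|---|
| 30% | 0.218 | 0.386 |
| 40% | 0.209 | 0.370 |
| 50% | 0.185 | 0.331 |

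With 3/10 at goal in one arm, 8/10 in the other gives Fisher p = 0.070 and 9/10 gives p = 0.020, so Fisher needs 9/10. For chi-square, 8/10 gives 20 × (3×2 − 7×8)²/(10×10×11×9) = 5.05, above 3.84. With 7/10 it is 20 × (3×3 − 7×7)²/(10×10×10×10) = 3.20, below it. Chi-square therefore needs 8/10.

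**4. Continuous arm comparison, same 1 SD difference.**
- Two-sample t on change, 18 df: noncentrality 1/√(2/10) = 2.24, power 0.562.
- ANCOVA, 17 df, residual SD √(1 − 0.25) = √0.75: noncentrality 1/(√0.75 × √0.2) = 2.58, power 0.682. In 20,000 simulated trials that allow chance baseline imbalance, power is about 0.66.

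**5. Precision of the arm difference (95% half-width).**
- Change score: 2.101 × SD × √0.2 = 9.4 mmHg (SD 10) to 14.1 mmHg (SD 15).
- ANCOVA: 2.110 × SD × √0.75 × √0.2 = 8.2 to 12.3 mmHg, slightly more with chance baseline imbalance.

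**6. A smaller effect.** For a 5 mmHg difference and SD 10–15, ANCOVA power is 13–23% and change-score power 11–19%. For a 0.5 SD shift, Fisher has about 5% and uncorrected chi-square about 12–13%.

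**The case against.** The strongest reply is that the plan poses one analysis question, goal attainment, and tests it between arms. Section 8 mentions control and reaching goal together, so control in Section 4 could mean goal attainment. On that reading the comparative aim already has its test. This stands for the goal question, and that test should stay. It does not cover the Specific Aim's question about similar results. The plan also chose to test continuous pressure, but by a method that cannot compare the arms.

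Second, this is a pilot, and Section 6 calls its tests descriptive. Group summaries are not excluded, and the plan never says it will set two p-values side by side. That is fair: the gap is that no arm estimate is specified, and the side-by-side harm is conditional. But these are inferential tests whatever they are called, and an effect estimate with its interval is the natural output of a pilot.

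Third, a 1 SD difference means 10–15 mmHg between arms, larger than the 4–10 mmHg falls assumed within arms. At 5 mmHg every method is weak. This stands. ANCOVA keeps its advantage, but the case rests on estimation more than on power. With half-widths of 8–12 mmHg and no similarity margin, the interval would seldom establish similarity. It would show that openly.

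Fourth, the documents do not choose 24-hour mean systolic pressure, and the Abstract lists office values before and after. The choice does belong to the investigators. One measure still has to be named.

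**Conclusion.** The concern holds. No section specifies a between-arm estimate or test of continuous blood pressure, although the aim is comparative and the recordings are planned in both arms. This follows from the text and needs no assumption.

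The consequences depend on assumed SDs, effects and correlation. Under identical strategies, by-arm testing produces one significant arm in 21–50% of trials. At a 1 SD difference, the goal count has 19–39% power depending on the test, against 66–68% for ANCOVA. The correction gives an honest estimate and does not make 20 patients adequate for modest differences. It should be fixed; the goal-attainment comparison itself remains sound.

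**What to change.** Keep the between-arm Chi-square or Fisher test for the goal question. Replace the paired t test as the inferential analysis of continuous pressure with text such as:

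> One-month 24-hour mean systolic ABPM pressure will be regressed on randomised arm and baseline 24-hour mean systolic pressure (ANCOVA), with patients analysed in their randomised arm. The arm difference will be reported with its 95% CI. Paired within-arm changes will be reported as description only. Recordings that fail the stated ABPM validity criteria will be listed by arm, and the result shown with and without them.

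If the investigators prefer another pressure measure, they should name it in place of 24-hour mean systolic. State the expected half-width (about 8–12 mmHg under the assumptions above) beside the analysis, so that a non-significant result is not read as similarity.

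The cost is wording: sample, visits, recordings and goal test do not change. One caveat applies. Section 9 lets the investigators analyse data as they accrue, so if any outcomes have already been seen, the new analysis should be labelled post hoc.
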